Official Title: Immediate Postplacental Intrauterine Device insertion in high-risk patients

Principal Investigator: [name], MPH

Professor, Department of Obstetrics and Gynecology Oregon Health & Science University

> NCT No. NCT02169869

Protocol Version Date: March 16, 2017

Protocol

Title: Immediate Postplacental Intrauterine Device insertion in high-risk patients

[name]

Research Advisors: [name], MPH; [name], MPH; [name], MPH

1. Background

Approximately half of all pregnancies in the United States are unintended.¹ With the transition to new parenthood, women in the postpartum period are particularly susceptible to unintended pregnancy. Recent data has shown that among women 18-24 years of age, 57% had a repeat pregnancy within 18 months of delivery.²

Intrauterine devices (IUD) provide safe, effective, and long acting reversible contraception (LARC). For those who desire an IUD after delivery, common practice in the United States is insertion at 6 weeks postpartum. However, women who plan an IUD often face barriers to receiving one for many reasons including loss of insurance coverage, difficulty getting to postpartum visits, and early repeat pregnancy.³ Immediate postplacental IUD insertion is defined as IUD insertion within 10 minutes of the expulsion of the placenta.⁴ Although this practice is common in developing countries, it is rare in the United States. There are several potential advantages to immediate IUD insertion including the cervix is already dilated, postplacental insertion is often performed under labor anesthesia therefore patients can avoid the potential discomfort related to IUD insertion, in addition, no additional visit is needed.

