Both the levonorgestrel and copper IUD provide contraception without interfering with breastfeeding.⁵ For women with limited access to medical care, hospitalization for delivery provides a unique opportunity to address the need for contraception. The major disadvantage to postplacental placement is an increase in expulsion rates; as high as 8-24% by 6 months. One study suggests that the rate of expulsion has to do with the insertion technique and provider experience.^{6,7} Despite this higher expulsion rate, continuation rates for IUD use at 6 months appear to be equivalent for postplacental IUD as compared to routine 6 week insertion. In a setting where women typically attend a postpartum follow-up visit where IUDs are routinely available, postplacental placement has not been shown result in higher uptake of IUDs or to be cost-efficient.⁶ However, in a population at high risk for lack of postpartum follow-up, the higher expulsion risk becomes less a concern, as the alternative to postplacental placement would be nonuse of contraception or use of a less effective method. *Identification of a group of postpartum* women at high risk for poor follow-up would enable targeted delivery of postplacental placement. Recent studies at our institution have shown women with a history of poor attendance to prenatal appointments are at high risk of not returning for routine postpartum IUD placement. 8,9 Based on these recent studies, we hypothesize that women with less than 10 prenatal visits or 2 or more no show visits who receive an immediate postplacental IUD will have higher rates of IUD continuation at 3 months than women who are scheduled to receive an IUD at a delayed postpartum visit.

2. Study Objective: To determine whether immediate postplacental IUD placement will improve IUD uptake at 3 month postpartum in women with a history of poor prenatal clinic attendance.

3. Study Design:

The study will be a randomized clinical trial. Women with less than 10 prenatal visits and/or 2 or more no show visits who desire an IUD will be considered for enrollment. If consented and meet inclusion criteria, they will be randomized after delivery to receive an IUD immediately postplacental or at their routine postpartum visit.

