Women who plan to deliver a live birth singleton via vaginal or cesarean delivery at OHSU hospital will be considered for inclusion in the study. Women who desire an IUD for postpartum contraception will be approached for study participation. The postpartum contraception plan is routinely documented during their prenatal course. It is also addressed by the obstetrical team upon admission to Labor & Delivery at OHSU. The obstetrical team will identify subjects who present in labor who meet the criteria of poor prenatal clinic attendance and express interest in intrauterine contraception. These women will be provided with information about the study, and if interested will be provided with informed consent counseling. Completion of the informed consent process and signing of the consent can be done before or after delivery depending on the individual circumstances of the labor. Subjects that meet all inclusion and no exclusion criteria, and agree to the terms of the study, will be entered into the study after a discussion of study procedures and signing the informed consent. Immediately after vaginal or cesarean delivery, consenting subjects will be randomized to immediate postplacental IUD placement or IUD placement at their routine postpartum visit. Women randomized to the immediate postplacental IUD group will receive their IUD within 60 minutes of placental delivery. To minimize interference with the early postpartum interval, all subjects will be asked to complete a demographic questionnaire at their convenience at some point prior to hospital discharge. Prior to discharge from the hospital women who received a postplacental IUD will be assisted in scheduling a routine postpartum visit with their primary provider. Subjects who are randomized for IUD insertion at their postpartum visit will be assisted in scheduling a postpartum visit and IUD placement with their usual obstetrical care provider. All subjects in the delayed group will be provided with contact information for the Women's Health Research Unit at OHSU. If a subject cannot obtain an IUD at her usual place of care, the device will be placed at no cost through the WHRU.

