 - ii. Schedule follow up appointment if needed
- c. IUD placement(IUD insertion postplacental or postpartum visit): Prior to IUD insertion, the provider will discuss informed consent with the patient and will sign a formal surgical consent form to be placed in the patient's medical chart. The IUD will be inserted as detailed in study procedures. Subjects receiving postplacental IUDs will be encouraged to have the IUD strings checked at their postpartum visit by their primary provider. All subjects will be counseled on how to check their IUD strings.
 - i. IUD insertion procedure
- d. Follow Up: At three months postpartum, participants will be contact by phone, text, or email. They will be asked whether they have had a known expulsion, pregnancy, or elective IUD removal. A brief questionnaire will include questions regarding ease of placement and overall satisfaction with the timing of placement. A study stipend will be provided at this time. Participants who did not follow up for IUD insertion or those that report IUD expulsion will be encouraged to contact their primary provider to discuss contraception. Chart review for confirmation of IUD placement will be performed.
 - i. Final questionnaire
 - ii. Study subject stipend paperwork
- **13. Data Analysis:** Data will be validated and entered into a computer. Statistical analysis will be carried out using STATA. Principal outcome measures include pregnancy and removal rates, cumulative expulsion, and continuation rates.
- 14. Data management: All patient data sheets will be kept confidential and in a locked office. A unique patient study identification number will be placed on the data forms. Study identification will be subject last initial and a unique three digit identifier. No subject names will be included with the study data. Study identifiers kept in a logbook will be assigned to each patient to protect confidentiality. For subjects who do not enroll, all screening documents will be kept in a locked office and password protected computer and confidentially destroyed once study is complete. When undergoing statistical analysis, the forms will be transferred to the primary investigator's locked office. Patient identifiers will be stored separately from the data files on the primary investigator's password-protected computer. Only the study investigators will have access to this identifier list.

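### Does the later insertion in the delayed arm spoil the expulsion and removal results, which are asked about once at 3 months after delivery?

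*Combined protocol and SAP*

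**What the plan says.** Section 7 names one primary outcome, the proportion of subjects using an IUD at 3 months, and bases the power statement on it. Section 13 gives a wider list: "Principal outcome measures include pregnancy and removal rates, cumulative expulsion, and continuation rates". It sets no time origin, denominator or censoring rule for these measures.

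Section 12d places the data collection at three months postpartum: "They will be asked whether they have had a known expulsion, pregnancy, or elective IUD removal". It adds "Chart review for confirmation of IUD placement will be performed". Neither sentence mentions the date of an event.

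The arms start their time at risk at different points. For the immediate arm, Section 3 says "Women randomized to the immediate postplacental IUD group will receive their IUD within 60 minutes of placental delivery". The delayed arm receives the device at the routine postpartum visit, with no week fixed. Section 1 notes that "common practice in the United States is insertion at 6 weeks postpartum". Delayed insertions are mostly done by usual-care providers (Section 11c), with a fallback in Section 3: "If a subject cannot obtain an IUD at her usual place of care, the device will be placed at no cost through the WHRU". Section 16 says that data obtained before withdrawal are analysed by intention to treat.

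**The concern.** Expulsion is the harm that matters most here. Section 1 calls it the major disadvantage of postplacental placement and puts it "as high as 8-24% by 6 months". Readers will want to compare it between arms.

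If the analyst divides expulsions by devices placed and compares arms at the 3-month contact, the delayed devices have had roughly half the time in which to be expelled. Identical devices would then show fewer expulsions in the delayed arm. The artefact runs in the same direction as the true difference that Section 1 expects, so the two could not be separated afterwards without dates. The same reasoning applies to removals, and to any continuation rate calculated only among women who received a device. Because there is one planned contact, dates not asked for then might be lost.

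**Working it through.** **The plan's own figure.** Inputs from Section 7: 20 per arm, 0.9 versus 0.5, power 81%. Two-sided 5% significance is assumed, since the protocol states no level. With pooled variance and mean proportion 0.7:

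z = [0.4 × √20 − 1.96 × √(2 × 0.7 × 0.3)] / √(0.9 × 0.1 + 0.5 × 0.5) = (1.789 − 1.270) / 0.583 = 0.89, so power is 81.3%.

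This agrees with 81%. The outcome is a yes/no status at a fixed time after delivery, so no insertion or event date enters it.

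**Inputs for the exposure check.**
- From the protocol: 8% to 24% postplacental expulsion by 6 months (Section 1); 50% in the delayed arm, which Section 7 ties to the rate of return, taken here as 10 devices among 20 women.
- Assumed: contact at 13 weeks, 6 months as 26 weeks, delayed insertion at week 6 (varied), constant hazard (varied), and, where stated, a 13-week risk of 10% or 3%.

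**Formula.** If a device has risk R over T weeks under a constant hazard, its risk over t weeks is 1 − (1 − R)^(t/T). The shortfall is 10 × (risk over 13 weeks − risk over the delayed exposure). For R = 10% and insertion at week 6: 1 − 0.9^(7/13) = 5.5%, and 10 × (0.1000 − 0.0552) = 0.45.

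| Scenario (same risk for both arms' devices, except the last row) | Risk over 13 weeks | Risk per delayed device | Shortfall, expected events in 10 devices |
|---|---|---|---|
| 10%, week 6 | 10.0% | 5.5% | 0.45 |
| 10%, week 4 | 10.0% | 7.0% | 0.30 |
| 10%, week 8 | 10.0% | 4.0% | 0.60 |
| 10%, week 6, front-loaded hazard (Weibull shape 0.5) | 10.0% | 7.4% | 0.26 |
| 8% by 6 months, week 6 | 4.1% | 2.2% | 0.19 |
| 24% by 6 months, week 6 | 12.8% | 7.1% | 0.57 |
| 24% by 6 months, week 8 | 12.8% | 5.1% | 0.77 |
| 24% by 6 months, week 10 | 12.8% | 3.1% | 0.97 |
| Delayed device's own risk 3%, week 6 | 3.0% | 1.6% | 0.14 |

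All but the last row give a delayed device a postplacental-type risk. Section 1 says postplacental placement raises expulsion, so a lower delayed-arm risk is the more likely case, and the shortfall shrinks with it. The 3% is only an example; the protocol gives no figure.

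If all 50 women are counted (25 per arm, 12.5 delayed devices), multiply by 1.25: 0.45 becomes 0.56, 0.77 becomes 0.96, and the week-10 case becomes 1.21.

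**Per randomised woman.** With 10% in the immediate arm, non-receipt alone takes the delayed arm to 10% × 0.5 = 5.0%, and shorter exposure takes it on to 5.5% × 0.5 = 2.8%. Both steps follow from the assigned strategy, and both belong in a comparison of strategies at 3 months.

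**Precision.** The exact 95% interval for 2 events in 20 devices is 1.2% to 31.7%. For 0 in 10 it is 0% to 30.8%. A shift of half an event in 10 devices is 5 percentage points.

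**The case for a change.** The best case for a change is that it would be cheap and the information perishable. At 13 versus 7 weeks the exposure ratio is 1.86, and equal hazards would give an apparent risk ratio of about 1.8 from the protocol's own expulsion range. A few date fields and a sentence on the time origin would allow a Kaplan-Meier summary from insertion, with late insertions censored early. The sample size and the primary would not be touched.

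Part of this stands. Section 13 is silent on the clock and the denominator, and having dates is better than not having them.

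The rest is weaker than it looks:

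- The argument calls shorter exposure a bias, yet accepts non-receipt as a real effect of assignment. Both come from the same assignment. Bias appears only if the target is an equal-time, per-device comparison. That comparison includes only the delayed-arm women who came back, so it is not protected by randomisation.
- The questionnaire and data forms are not in the document. Section 12d summarises the questions and does not list the fields, so it cannot be said that dates are absent.
- Insertion dates are probably recoverable. Delivery fixes the immediate arm's date. For insertions generally, Section 12c calls for a consent form in the chart beforehand, and a chart review is planned. Insertion outside the study clinic makes this less certain for some women.
- Kaplan-Meier on about 10 delayed devices would rest on recalled dates of noticed events. Section 12c says "Subjects receiving postplacental IUDs will be encouraged to have the IUD strings checked at their postpartum visit by their primary provider", so events may be noticed earlier in that arm, which adds a timing difference of its own. Counts with the number of devices placed tell a reader nearly as much.

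**Conclusion.** No change to the plan is needed. Section 13 leaves out a detail that an analyst would fill sensibly: report expulsions and removals by 3 months postpartum per randomised woman, give the number of devices placed in each arm, and treat any per-device figure as descriptive. That reading fits the fixed-time contact and the intention-to-treat statement in Section 16. The primary outcome, its power and the trial's main conclusion do not depend on it.

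A naive per-device comparison would understate delayed-arm expulsions by about 0.1 to 0.6 of one expected event at 20 per arm. That range assumes contact at 13 weeks, 10 delayed devices and insertion at 4 to 8 weeks, with one factor varied at a time. The highest protocol expulsion rate with insertion at week 8 or 10 raises it to 0.77 or 0.97; at 25 per arm only the week-10 case passes one event (1.21). With intervals reaching about 31%, none of this would alter an inference. The removal part is unquantified, since the documents give no removal rate.
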